2.2.2. Secondary Endpoints (Efficacy)

(Assess at Baseline, Day 3, 7, 14, and 28, and Month 3, 6 and 12 following IV allogeneic MSC infusion)

1. Assess EPC-colony forming units (CFUs)
2. Assess circulating inflammatory markers (IL-1, IL-6, TNF α , and CRP)
3. Assess circulating angiogenic factors known to mobilize and recruit EPCs (VEGF, SDF-1 α , and SCF)
4. Assess FMD%

3. STUDY DESIGN

3.1 Description of the Study

Sixteen (16) diabetic subjects with endothelial dysfunction will be scheduled to undergo a peripheral intravenous infusion after meeting all inclusion/exclusion criteria at baseline. The study will consist of a Pilot Phase and Randomized Phase.

PILOT PHASE

To test the safety of allogeneic mesenchymal stem cells therapy for endothelial dysfunction in diabetes subjects administered via peripheral intravenous infusion, a non-randomized, unblinded pilot phase of six subjects will be performed.

Three (3) subjects will be treated with 20 million (20×10^6) allogeneic hMSCs
Three (3) subjects will be treated with 100 million (100×10^6) allogeneic hMSCs.

The three (3) subjects in the low dose group will not be treated less than 5 days apart and will each undergo full evaluation during those five days to show that there are no signs of treatment emergent SAE's before continuing with the treatment of further subjects.

The three (3) subjects in the high dose will not be treated until the three (3) subjects in the low dose have completed their one-month follow-up assessments and safety measures have been reviewed to confirm that there have been no treatment emergent SAE's. In addition, the first three (3) subjects in the high dose group will not be treated less than 5 days apart.

RANDOMIZED PHASE

After the Pilot Phase, the Randomized Phase will begin. Ten (10) diabetic subjects with endothelial dysfunction will be randomized to undergo a peripheral intravenous infusion in a 1:1 ratio after meeting all inclusion/exclusion criteria at baseline.

Five (5) subjects will be treated with 20 million (20×10^6) allogeneic hMSCs Five (5) subjects will be treated with 100 million (100×10^6) allogeneic hMSCs

The Allo-hMSCs will be supplied from an allogeneic human mesenchymal stem cell source manufactured by the University of Miami.

Electronic randomization will be performed by the University of Miami Biostatistics Collaboration and Consulting Core (BCCC) and communicated to cellular laboratory personnel who have no contact with the investigators or subjects. After each infusion, subjects will be monitored for immediate complications.

Continued safety and tolerability with review of adverse events (AEs) will be monitored at each visit. Efficacy parameters (EPC's, FMD%, and inflammatory markers) will be assessed at baseline, Day 3, 7, 14, and 28, Month 3, Month 6 and Month 12 following the IV infusion of the allocated investigational product. Clinical laboratory tests to assess safety will be performed at every clinic visit, excluding the screening visit.

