Follow up: Subjects will be followed at 3, 7, 14 and 28 days to evaluate the dose and timing of the stimulatory effect of MSCs on circulating angiogenic factor levels, EPC function, and FMD%, and at 3, 6, and 12 months post-infusion to complete all long-term safety and efficacy assessments.

Route of Administration: Peripheral Intravenous Infusion

Duration of Study participation: Approximately 12 months

Definition of Endpoints:

Safety (Primary): Incidence (at one-month post infusion) of any treatment-emergent serious adverse events (TE-SAEs), defined as the composite of: death, non-fatal pulmonary embolism, stroke, hospitalization for worsening dyspnea and clinically significant laboratory test abnormalities, determined per the Investigator's judgment.

Efficacy (Secondary): (Assess at Baseline, Day 3, 7, 14, 28, and Month 3, 6, and 12 following IV allogeneic MSC infusion)

1. Assess EPC-colony forming units (CFUs)
2. Assess circulating inflammatory markers (IL-1, IL-6, TNF α , and CRP)
3. Assess circulating angiogenic factors known to mobilize and recruit EPCs (VEGF, SDF-1 α , and SCF)
4. Assess FMD%

Major Inclusion Criteria:

- Be ≥ 21 and ≤ 90 years of age.
- Provide written informed consent.

- Have endothelial dysfunction defined by impaired flow-mediated vasodilation (FMD <7%).
- Have DM type 2 documented by hemoglobin A1C $\geq 7\%$ OR on medical therapy for diabetes.
- Females of childbearing potential must use two forms of birth control for the duration of the study. Female subjects must undergo a serum pregnancy test at screening and within 36 hours prior to infusion.

Major Exclusion Criteria:

- Be younger than 21 years or older than 90 years of age.
- Have a baseline glomerular filtration rate <35 ml/min $1.73m^2$ estimated using the MDRD formula.
- Have an ejection fraction $<45\%$ by gated blood pool scan, two-dimensional echocardiogram, cardiac MRI, cardiac CT or left ventriculogram within the past year, as documented by medical history.
- Have poorly controlled blood glucose levels with hemoglobin A1C $\geq 8.5\%$.
- Have a history of proliferative retinopathy or severe neuropathy requiring medical treatment.
- Have a hematologic abnormality as evidenced by hematocrit $< 25\%$, white blood cell $< 2,500/\mu l$ or platelet values $< 100,000/\mu l$ without another explanation.
- Have liver dysfunction, as evidenced by enzymes (AST and ALT) greater than three times the ULN.

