8.1 Screening Visit

See Table 1 for the procedures and assessment to be performed during the screening visit of the study, which can take place over several days. All screening visit test and procedures will occur upon signing the informed consent form (ICF). No screening exams will take place until the subject is fully informed of the research and signs the consent form.

All subjects will be enrolled at the University of Miami (UM) hospital and clinics. At the time of enrollment, we will review the medical records to ensure that the ADA guidelines for diabetic care are being followed. We will inform the subjects' primary care physician that the subject is enrolled in our study and must continue to follow the ADA guidelines throughout the trial. All the investigators follow these guidelines, and monitoring of the subjects' care by the clinical investigator or principal investigator will be ongoing through the trial at each follow visit.

Physical exam

A complete physical examination will include general appearance, skin, head and neck, Lymph nodes, musculoskeletal/extremities, cardiovascular, chest/lungs, abdomen, and neurological assessment. At screening, information about the physical examination and any significant findings must be recorded in the source documentation at the study site.

Vital signs

Vital sign measurements will be performed at least once on each study visit up to time of discharge. These measurements will consist of height (screening only), weight, respiratory rate, heart rate, blood pressure, oxygen saturation, and temperature. Respiratory rate, heart rate, and blood pressure should be measured in a seated position.

Endothelial function

- Brachial ultrasound testing and blood collection will be performed to assess endothelial function in the diabetic population at screening, baseline and 3 days, 7, 14, 28 days, 3 months, 6 months, and 12 months post stem cell infusion. This will help provide cumulative data in assessing whether or not stem cell infusion improves endothelial function. This test will be done in the morning prior to 12p.m.

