8.2 Baseline Visit

See Table 1 for the procedures and assessment to be performed during the baseline visit of the study. This visit will occur after all screening tests are completed and it has been determined that the subject meets eligibility criteria. This visit should occur within 2 weeks prior to Day 0 (the infusion visit).

The following endothelial function tests will be performed:

- Brachial ultrasound testing and blood collection will be performed to assess endothelial function in the diabetic population at screening, baseline and 3 days, 7, 14, 28 days, 3 months, 6 months, and 12 months post stem cell infusion. This will help provide cumulative data in assessing whether or not stem cell infusion improves endothelial function.
- Flow Mediated Diameter percent change (FMD%): All measurements of the brachial artery diameter and FMD will be performed in the morning, in a quiet and dark room and at controlled ambient temperatures between 20°C and 26°C. Studies will be conducted after an overnight fast of at least 10 hours (water is permitted), with the subject's supine and after 10 minutes of rest. The subject's right arm will be comfortably immobilized in an extending position, allowing for ultrasound scanning of the brachial artery 5–10 cm above the antecubital fossa. In each examination, recording of vessel images will be followed by inflation of a cuff to supra-systolic pressure (40 to 50 mmHg above systolic pressure) for 5 minutes. Then the cuff will be deflated and the brachial artery diameter will be imaged and recorded for 3 minutes. FMD% more than 10% is considered a normal response. Lower than 7% FMD% reflects endothelial dysfunction, which means a high likelihood to develop cardiovascular event in the future. Subjects with negative FMD% results (the artery is constricted after stress and not dilated as was expected) have the worst prognosis.
- Blood drawn from fasting subjects for biomarker and PRA analysis will be separated and the serum will be frozen until processed as one batch towards the end of the study.

- **Biomarker analysis:** Soluble pro inflammatory cytokines (interleukin 1, interleukin-6, tumor necrosis factor alpha, high-sensitivity C Reactive Protein, and circulating angiogenic factors) (VEGF, SDF-1 α , and SCF) using immunological and ELISA methods.

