8.3 Day 0 Visit

See Table 1 for the procedures and assessment to be performed during the Day 0 visit of the study. The Day 0 visit will occur after all baseline tests are completed and it has been determined that the subject remains eligible. Once the subject is deemed eligible to continue in the study, the subject will be administered the investigational product.

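### The protocol conflicts on whether FMD <7% must be met again at Baseline; if it must, and Baseline is the reference, regression to the mean can produce a spurious within-dose FMD rise

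*Combined protocol and SAP*

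**What the plan says.** FMD below 7% is an inclusion criterion (synopsis; Section 4.1). Brachial ultrasound is done "at screening, baseline and 3 days, 7, 14, 28 days, 3 months, 6 months, and 12 months post stem cell infusion" (Section 8.1). Table 1 puts Screening 1 to 6 weeks before Baseline, and Baseline 0 to 14 days before Day 0.

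Three places bear on when eligibility is decided:

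- **Section 3.1**, with matching text in the synopsis: subjects "undergo a peripheral intravenous infusion after meeting all inclusion/exclusion criteria at baseline". The condition is repeated for the randomized phase.
- **Section 8.3**: "The Day 0 visit will occur after all baseline tests are completed and it has been determined that the subject remains eligible".
- **Section 8.2**, on the Baseline visit: "This visit will occur after all screening tests are completed and it has been determined that the subject meets eligibility criteria".

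Sections 2.2.2 and 3.1 list the efficacy time points for FMD as Baseline, Days 3, 7, 14 and 28, and Months 3, 6 and 12. Screening is not among them. Section 8.2 gives the purpose of the scans as "assessing whether or not stem cell infusion improves endothelial function". Section 10.2 provides descriptive statistics and two-sided tests at 0.05 without multiplicity adjustment. It defines neither a change score nor a reference value. All 16 subjects receive cells, and both randomized arms are active.

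**The concern.** A site that follows Sections 3.1 and 8.3 would turn away a subject who reads 6.5% at Screening and 7.5% at Baseline. It would keep a subject whose true FMD is 7.5% but who happens to read 6.5% on both days. The Baseline values of those infused would then be selected to be low, partly through measurement error. That error is not carried to later visits, so the group mean would rise without any treatment effect.

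The rise would be complete at the first post-infusion scan and would persist to Month 12. That is also the pattern a fast, lasting effect would give. With no untreated or placebo arm, nothing in the trial separates the two. Section 6.6 sends the 28-day FMD results to the DSMB and the FDA and uses them to design the next protocol, so an inflated pre/post change could be carried forward.

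**Working it through.** **The passages.** Section 3.1 and the synopsis attach all criteria to baseline, and Section 8.3 asks for continued eligibility after the baseline tests. As Table 1 is laid out, brachial FMD is the only Baseline test tied to a numeric entry criterion. A second FMD gate is therefore the natural reading of these texts. Section 8.2 points the other way, and no sentence names FMD as re-judged. The documents do not settle it.

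**Inputs.** The threshold (7%), the visit schedule and the absence of an untreated arm come from the protocol. It gives no FMD mean, SD or repeatability, and Section 10.1 has no sample-size calculation, so there is no figure to reproduce. Assumed: mean μ of the screened population 5 to 7%, between-subject SD b of 2 to 3 points, test-retest SD e of 1 to 2 points, errors independent between visits, no treatment effect.

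**Notation.** SD = √(b² + e²); ρ = b²/SD²; c = (7 − μ)/SD; k = c√((1 − ρ)/(1 + ρ)). φ and Φ are the normal density and distribution function, and Φ₂ is the bivariate normal probability that both readings lie below c.

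**Gate at Screening only.** The Baseline error plays no part in selection, so the expected change from Baseline is 0.00.

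**Gate at Screening and Baseline.** Expected change = SD(1 − ρ)·φ(c)·Φ(k)/Φ₂(c,c;ρ).

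| Case | μ, b, e | SD, ρ, c | Calculation | Change (points) |
|---|---|---|---|---|
| Low | 5, 3, 1 | 3.162, 0.900, 0.632 | 0.3162 × 0.3266 × 0.5577 / 0.6779 | 0.08 |
| Middle | 6, 2.5, 1.5 | 2.915, 0.735, 0.343 | 0.7717 × 0.3762 × 0.5533 / 0.5228 | 0.31 |
| High | 7, 2, 2 | 2.828, 0.500, 0 | 1.414 × 0.3989 × 0.5 / 0.3333 | 0.85 |

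Simulation agrees. The formula has no visit term, so the shift is the same at all seven post-infusion visits. The mean Baseline FMD over these scenarios is about 3 to 5%.

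**Wider assumptions** (mean 4 to 8%, total SD 2 to 4, test-retest correlation 0.4 to 0.8): the shift is positive in all 27 scenarios, from 0.04 to 1.80 points. With mean 6, SD 3 and correlation 0.6 it is 0.52 points. One paired t-test at one visit, used only as an illustration because the plan names no such test, would then show a false improvement in 11.6% of trials with n = 16, 7.0% with n = 8 and 5.1% with n = 5, against a nominal 2.5%. The randomized dose difference has bias 0.00 and rejects in 5.0%.

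**Consequences of a Screening-only gate** (first set of assumptions):

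- Share reading 7% or more at Baseline = 1 − Φ₂/Φ(c). Low: 1 − 0.6779/0.7365 = 8%. High: 1 − 0.3333/0.5 = 33%.
- Spurious Screening-to-Baseline rise = SD(1 − ρ)φ(c)/Φ(c). Low: 0.3162 × 0.3266/0.7365 = 0.14. High: 1.414 × 0.3989/0.5 = 1.13.

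**The case against.** The strongest reply is that the protocol uses the word baseline loosely, for any time before infusion. Coagulation and viral serology bear on exclusion criteria but are done at Screening. The renal exclusion speaks of a baseline filtration rate, while Table 1 places chemistry at Screening and Day 0. Remaining eligible can refer to the pregnancy test within 36 hours of infusion or to a new illness. This stands as a reason for caution. A reader might infer that the protocol plainly requires FMD <7% a second time and that a false improvement will follow. The documents do not support that: Section 8.2 contradicts the second gate, the Baseline reference is inferred rather than written, and under a Screening-only gate the bias is zero. The reply does not remove the conflict between the sections.

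The second reply concerns size. In the middle case the standard error of a mean change is about √2 × 1.5/√8 = 0.75 points for one dose and √2 × 1.5/√16 = 0.53 for all 16 subjects, so a shift of 0.31 is less than one standard error. This also stands. The bias is systematic but need not dominate the result, and it is negligible if most screened subjects lie well below 7% and repeatability is good.

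Third, a reader might infer that the choice of dose and time point in Section 6.6 is compromised. It is not: the shift is expected equally in both doses and at every post-infusion visit. Only the level of change from Baseline is affected, in an endpoint that Section 10.2 calls exploratory; the primary endpoint is safety.

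**Conclusion.** The concern holds conditionally. The synopsis and Sections 3.1 and 8.3 conflict with Section 8.2 on whether the Baseline FMD decides entry, and they must be reconciled. If the Baseline scan is both gate and reference, the expected spurious rise is about 0.1 to 0.85 FMD points, about 0.3 mid-range, at every visit from Day 3 to Month 12. The direction is certain under that reading. The size rests wholly on the assumed mean, SD and repeatability. The bias is confined to within-dose and pooled pre/post FMD change. It is worth correcting because the stated purpose of the scans is to judge improvement, no arm would reveal the artefact, and the remedy is wording.

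**What to change.** In the synopsis and Sections 3.1 and 8.3, state, in line with Section 8.2, that the FMD <7% criterion is judged on the Screening scan only and that the Baseline FMD does not decide eligibility. In Section 10, name the separate Baseline scan as the reference for FMD change.

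This needs no extra scans. Its cost is that 8 to 33% of subjects passing Screening would have a Baseline FMD of 7% or more, under the assumptions above; the sponsor should accept this explicitly. If a second gate is wanted, the reference should be another pre-infusion scan not used for selection, at the price of one more scan per subject. Averaging Screening and Baseline does not help when both are gates: with mean 6, SD 3 and correlation 0.6 the shift stays at 0.52.

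The Screening-to-Baseline change should not be presented as an untreated control interval. Under a Screening-only gate it contains the regression to the mean, about 0.14 to 1.13 points, and setting it against post-infusion change could make a real effect look smaller. It may be reported only as a gauge of that artefact. The fix removes this one source of bias; without a concurrent control, a pre/post rise still cannot be attributed to the cells on that evidence alone.

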| 
Design and Investigational Plan:
 
To evaluate the role of allogeneic mesenchymal stem cells therapy for endothelial dysfunction in diabetes.
 
Sixteen (16) diabetic subjects with endothelial dysfunction will be scheduled to undergo a peripheral intravenous infusion after meeting all inclusion/exclusion criteria at baseline.
 
PILOT PHASE (Unblinded):
 
The dose for subjects in the pilot phase will vary from 20 million cells to 100 million cells and will be Unblinded, with subjects and study team members aware of the doses administered to the subject. The pilot phase will consist of:
 
Three (3) subjects will be treated with 20 million (20×10^6) allogeneic hMSC's Three (3) subjects will be treated with 100 million (100×10^6) allogeneic hMSC'
 
The three (3) subjects in the low dose group will not be treated less than 5 days apart and will each undergo full evaluation during those five days to show that there are no signs of treatment emergent SAE's (TE-SAE) before continuing with the treatment of further subjects.
 | |

The three (3) subjects in the high dose will not be treated until the three (3) subjects in the low dose have completed their one-month follow-up assessments and safety measures have been reviewed to confirm that there have been no treatment emergent SAE's. In addition, the three (3) subjects in the high dose group will not be treated less than 5 days apart.

Randomized Phase (Double-Blind):

After the pilot phase, subjects will be randomized to one of two treatments in a 1:1 fashion. This phase of the study will be blinded to both subjects and study team members. The randomized phase will consist of ten (10) diabetic subjects with endothelial dysfunction will be subsequently randomized to undergo a peripheral intravenous infusion after meeting all inclusion/exclusion criteria at baseline:

Five (5) subjects will be treated with 20 million (20×10^6) allogeneic hMSC's and Five (5) subjects will be treated with 100 million (100×10^6) allogeneic hMSC's

The Allo-hMSCs will be supplied from an allogeneic human mesenchymal stem cell source or commercial clinical grade bone marrow source manufactured by the University of Miami.

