9.2.4 Subject Stopping Guidelines

This guideline is to be used to indicate boundaries requiring discussion by the Data and Safety Monitoring Board (DSMB) and is designed to assist the independent DSMB in

overseeing the study. The DSMB may also request additional interim analyses and develop other criteria including provision for monitoring of potential late effects to determine when to intervene in the enrollment or treatment of subjects in the study.

The first more conservative stopping guideline is to monitor subjects for unexpected SAEs where there is a reasonable possibility that the study product or administration procedure caused the event within 30 days of administration including cardiorespiratory distress during infusion, subject death, myocardial infarction, hemodynamically unstable ventricular tachycardia, stroke, or more than two related, \geq Grade 3 AEs (based on the NIH CTCAEv4). Study accrual and further treatment of subjects will be put on hold (temporary suspension of study drug administration, pending a safety investigation) if any subjects experience one of these events. The DSMB will be notified within 24 hours of the occurrence of these events and will be convened within 3 business days to review the event and study.

The following are subject stopping guidelines:

- Any subject who develops persistent (that is, still existing more than 3 hours after the end of IP infusion) cardiorespiratory signs or symptoms (for example, shortness of breath, tachypnea, tachycardia, hypotension, or palpitations) will continue with all scheduled follow-up if such follow-up is considered safe in the opinion of the Investigator.
- Any subject whose infusion is stopped due to cardiorespiratory distress will receive no further IP infusions but will continue with all scheduled follow-up if such follow-up is considered safe in the opinion of the Investigator.
- Any subject who develops any sign or symptom that, at the discretion of the Investigator, warrants the discontinuation of infusion will receive no further IP infusions but will continue with all scheduled follow-up if such follow-up is considered safe in the opinion of the Investigator.
- Infusion of the IP may be stopped if there is an adverse event that the Investigator believes is related to the IP or if there is an issue with the IP infusion.

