10.3 Interim Analyses

Interim analyses will be conducted at times coincident with regularly scheduled meetings of the Data and Safety Monitoring Board (DSMB) at approximately six-month intervals. The DSMB Chair will be notified each time an SAE occurs. After all subjects in the low dose have been followed for 30 days, at that time an independent DSMB will review all available data to make an independent recommendation to either keep the specified randomized dose 1:1 or to recommend a dose modification.

Policies of the DSMB will be described in the DSMB Charter, which will be prepared by the DSMB prior to study initiation. The stopping guidelines serve as a trigger for consultation with the DSMB for additional review, and are not formal “stopping rules” that would mandate automatic closure of study enrollment.”

11 Data Safety and Monitoring Board (DSMB)

NHLBI Gene and Cell Therapy Data and Safety Monitoring Board

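### The documents plan no one-month safety review of the three 100-million-cell pilot subjects before randomization opens, and the DSMB's recommendation on the randomized dose is triggered by low-dose follow-up

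*Combined protocol and SAP*

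**What the plan says.** The Synopsis (Design and Investigational Plan) and section 3.1 describe a six-subject unblinded pilot, three at 20 million cells and then three at 100 million, followed by ten subjects randomized 1:1 between the two doses.

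- **Within the low-dose pilot.** Subjects are dosed at least 5 days apart, and they "will each undergo full evaluation during those five days to show that there are no signs of treatment emergent SAE's" before the next is treated.
- **Low to high dose.** High-dose dosing waits until all three low-dose subjects have finished one-month assessments and a review has confirmed no treatment-emergent SAEs (TE-SAEs).
- **Within the high-dose pilot.** The Synopsis says "In addition, the three (3) subjects in the high dose group will not be treated less than 5 days apart". Section 3.1 says "the first three (3) subjects in the high dose group will not be treated less than 5 days apart". Neither attaches the five-day evaluation.
- **Pilot to randomized phase.** "After the Pilot Phase, the Randomized Phase will begin". The end of the Pilot Phase is not defined.
- **DSMB dose review (section 10.3).** The timing is given as "After all subjects in the low dose have been followed for 30 days, at that time an independent DSMB will review all available data". The stated purpose of that review is "to make an independent recommendation to either keep the specified randomized dose 1:1 or to recommend a dose modification".

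The primary endpoint (section 2.2.1) is TE-SAE incidence at one month after infusion.

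**The concern.** The plan guards entry to the higher dose but sets no matching condition for expanding it. Read literally, it lets subjects be randomized to 100 million cells before the primary safety endpoint is known in anyone given that dose in this trial. The one scheduled DSMB decision about the randomized dose is timed by the other dose group, so it need not draw on high-dose data. Once randomization opens, subjects and study personnel are blinded to dose (section 6.6). The unblinded pilot is therefore the investigators' clearest look at the high dose.

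**Working it through.** **Plan's own count.** 3 + 3 + 5 + 5 = 16, as stated in section 3.1. Section 10.1 gives no formal sample-size justification, so there is no power figure to reproduce.

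**Conditions at the two steps**

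| Condition | Low to high dose | High-dose pilot to randomization |
|---|---|---|
| At least 5 days between subjects | yes | yes |
| Five-day TE-SAE evaluation | yes | not stated |
| One-month follow-up complete | yes | not stated |
| Safety review with no TE-SAE | yes | not stated |
| Event-driven hold (section 9.2.4) | yes | yes |

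**When the section 10.3 review falls.** The text does not say which low-dose subjects it means.

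- *The three pilot subjects.* The Day 28 visit has a ±2-day window, so the one-month visit can be done on day 26 and the first high-dose infusion can follow at once. The DSMB trigger comes at day 30. The lead is 30 − 26 = 4 days, which is less than the 5-day spacing. At most one high-dose subject can have been dosed by then, with at most 4 days of follow-up.
- *All eight low-dose subjects.* The five randomized low-dose subjects have already been treated, which is too late to set the randomized dose.

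**Fastest permitted timeline (one month taken as 28 days).** Low-dose infusions fall on days 0, 5 and 10. High-dose infusions fall on days 10 + 28 = 38, then 43 and 48. Randomized dosing can start on day 48. Adding a one-month gate moves that to 48 + 28 = 76. Taking one month as 26 or 30 days throughout gives day 72 or day 80.

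**High-dose follow-up at opening.** Let *s* be the spacing of high-dose infusions and *g* the days from the third infusion to opening. Follow-up is min(30, 2s+g) + min(30, s+g) + min(30, g), out of 3 × 30 = 90 subject-days.

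| s, g | Follow-up | Share of 90 |
|---|---|---|
| 5, 0 | 10 + 5 + 0 = 15 | 17% |
| 7, 7 | 21 + 14 + 7 = 42 | 47% |
| 14, 14 | 30 + 28 + 14 = 72 | 80% |
| any s, g ≥ 30 | 90 | 100% |

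**Chance that a TE-SAE has appeared by opening, row (5, 0).** The documents give no event rate, so the 30-day rate *p* is assumed. Let *f* be the fraction of cumulative hazard that falls on infusion day, with the rest uniform over 30 days. All three subjects have passed infusion day, and together they have 15/30 = 0.5 of a subject-window of later follow-up. The chance is 1 − (1 − p)^(3f + 0.5(1 − f)). With full follow-up it is 1 − (1 − p)³.

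| p | f = 0 | f = 0.5 | f = 0.8 | Full 30 days |
|---|---|---|---|---|
| 10% | 5.1% | 16.8% | 23.2% | 27.1% |
| 5% | 2.5% | 8.6% | 12.0% | 14.3% |

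**What a clean gate would show.** With 0 of 3 events, the one-sided 95% upper limit is 1 − 0.05^(1/3) = 63%.

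**The case against.** The strongest reply is that the pilot is described in sections 3.1 and 6.6 as a test of safety, and safety is judged at one month. A reader may take the Pilot Phase to be over only when one-month follow-up is complete. That is a natural reading, but the text does not state it, whereas it does state the condition for the step before. The fastest schedule also needs minimum spacing, no pause and pre-screened subjects waiting, and later randomized subjects would be treated with more pilot follow-up in hand.

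The safeguards are real and not specific to dose. Section 9.2.4 suspends accrual for "unexpected SAEs where there is a reasonable possibility that the study product or administration procedure caused the event". Because section 9.15 classes all AEs as unexpected, that qualifier excludes nothing. The same section monitors the TE-SAE proportion within 30 days, section 6.5.3 checks key safety endpoints against a threshold, and section 10.3 says "The DSMB Chair will be notified each time an SAE occurs". These reduce the risk but do not replace a gate, because they respond to events. The hold also requires possible causation, whereas the low-dose gate requires no TE-SAE at all.

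Prior data also count. Section 6.3 cites earlier trial data in support of the doses. Section 6.4 reports earlier rates of up to 30 million cells per minute without infusion toxicity, against a maximum of 2.5 million here. The protocol gated escalation despite those data.

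Finally, section 11.12 places the final statistical monitoring plan in a Charter appendix that is not provided. A gate may exist there.

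**Conclusion.** The visible text makes neither one-month follow-up nor a safety review of the three high-dose pilot subjects a condition for opening randomization. On neither reading does the section 10.3 trigger wait for high-dose follow-up. This should be fixed.

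The size depends on accrual. At worst, 15 of 90 subject-days are in hand and nobody at 100 million cells has reached the endpoint. If opening falls 30 days or more after the third infusion, there is no gap. If most risk falls on infusion day, little detection is lost: 23.2% against 27.1% at an assumed 10% rate with f = 0.8. Even a clean gate is clinical caution and not statistical assurance, given the 63% limit.

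A reader might infer more than the documents support in three ways:

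- *That high-dose subjects go unmonitored.* They do not, since the event-driven hold and SAE notification cover them.
- *That nobody can have received 100 million cells when the DSMB makes its recommendation.* The visit window allows one subject a few days earlier.
- *That the sections contradict each other.* They leave a gap that an explicit definition would close.

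**What to change.** In the Synopsis and section 3.1:

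1. Apply the five-day TE-SAE evaluation between the three high-dose pilot subjects.
2. State that the Pilot Phase ends, and randomization may open, only when all three have completed Day 28 and their safety measures have been reviewed.

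In section 10.3, trigger the DSMB's recommendation to keep or modify the randomized dose when all six pilot subjects have 30 days of follow-up, by ad hoc conference call if no meeting is due. Keep the low-dose 30-day review as the escalation review. One review can serve both the opening of randomization and the dose recommendation. If the Charter appendix already contains such a gate, a sentence pointing to it in section 3.1 covers the first change.

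The cost on the tightest schedule is 28 to 30 days of follow-up plus 14 days, because section 11.6 asks for materials two weeks ahead. That is 42 to 44 days, or about six weeks. Waiting for the written Summary Report (up to 30 days, section 11.6.2) would make it 72 to 74 days. Waiting for a scheduled meeting, usually held twice a year, could take longer still. Slower accrual absorbs part of the delay. No subjects or visits are added.
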